Insufficient vitamin D (vitD) has been linked to a large number of pathologies including immune disorders and infectious diseases. VitD functions as a key host defense regulator against viral pathogens. High levels of vitD in the blood have been associated with resistance to human immunodeficiency virus type 1 (HIV1) infection. Moreover, low levels of vitD have been associated with higher levels of immune activation and inflammation in HIV and other diseases. While the results of clinical trials studying vitD supplementation have differed, there are several well-designed, large meta-analyses that have supported vitD supplementation as safe and protective against acute respiratory tract infections, with those that were severely vitD deficient receiving the most benefit.

The innate immune response in antigen-presenting cells (monocyte/macrophages and dendritic cells) is initiated and perpetuated by pathogen-associated molecular patterns (PAMPs) of the infecting virus interacting with pattern recognition receptors (eg, Toll-like receptors [TLR]). TLR activation leads to up-regulation of expression of the intracellular vitD receptor (VDR) and CYP27B1 (25-hydroxyvitamin D [25D]-1 α -hydroxylase); the latter event up-regulates local generation of the active vitD metabolite, 1,25-dihydroxyvitamin D (1,25D). 1,25D can then engage the VDR in an intracrine mode, which, in turn, controls cathelicidin antimicrobial peptide (*CAMP*) and interleukin 1 β (IL-1 β) gene expression, IL-1 β being a central initiator of the adaptive immune response.

LL37 is a potent, central, endogenously synthesized antimicrobial protein in humans, the product of the *CAMP* gene. Early in infection, LL37 is made principally by innate immune cells, monocyte/macrophages and dendritic cells, initiators of the immune response to both bacterial and viral infections. Owing to serendipity, a retrotransposon bearing a perfect vitD

response element (VDRE: AGGTCAXXXAGGTCA) was inserted into the promoter of the cathelicidin gene in great apes and humans. This ancient event made LL37 production dependent on transactivation of *CAMP* by the 1,25D-activated VDR.

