COVID-19 patients are expected to (but may not) present with serum total 25D levels averaging approximately 20-25 ng/mL, unless vitD becomes acknowledged as a possible prophylaxis against SARS-CoV-2 infection, based on information gathered from OPKO's prior PK studies conducted in healthy US volunteers and based on information from many US studies published in the medical literature. CKD is known risk factor for COVID-19 and patients with CKD will present with even lower 25D levels as advancing kidney disease is known to be associated with declining 25D levels [Levin et al 2007]. Phase 3 studies conducted by OPKO in large numbers of patients with stage 3-4 CKD have shown that baseline serum total 25D levels average below 20 ng/mL [Sprague et al 2016]. Further, these studies have shown that Rayaldee is safe in the CKD population at the proposed doses.

Few studies, to date, focused on treating COVID-19 have included CKD patients and many ongoing studies with anti-viral therapies have specifically excluded such patients. COVID-19 disproportionately affects patients with underlying disorders, and a significant percentage of COVID-19 patients have underlying CKD. Therefore, CKD patients with COVID-19 are available for recruitment and will be allowed to participate in the present study. Many subjects in each arm of this study may, therefore, have stage 3 or 4 CKD, defined as an estimated glomerular filtration rate (eGFR) of 15 to <60 mL/min/1.73m².

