12.3 Pharmacokinetics

Absorption

No food effect study was conducted with 30 mcg and 60 mcg doses of RAYALDEE. However, a food effect study with a supratherapeutic dose of 450 mcg in healthy subjects showed an approximately 5-fold increase in maximum serum calcifediol concentration (C_{max}) and a 3.5-fold increase in AUC_{0-t} when RAYALDEE was administered with a high fat, high calorie meal compared to fasting.

Exposure to calcifediol increased proportionally over the dose range of 30 to 90 mcg following repeated daily administration of RAYALDEE at bedtime to subjects with secondary hyperparathyroidism, chronic kidney disease and vitamin D insufficiency. Steady-state levels of serum total 25-hydroxyvitamin D are reached after approximately 3 months [see Clinical Studies (14)].

Distribution

Calcifediol is extensively bound to plasma proteins (>98%). The mean apparent volume of distribution is 8.8 L in healthy subjects following a single oral dose of RAYALDEE, and 30.1 L in subjects with stage 3 or 4 chronic kidney disease following repeated dosing.

Elimination

The mean elimination half-life of calcifediol is approximately 11 days in healthy individuals following a single dose of RAYALDEE, and approximately 25 days in patients with stage 3 or stage 4 chronic kidney disease following repeated once daily dosing.

Metabolism

Production of calcitriol from calcifediol is catalyzed by the 1-alpha-hydroxylase enzyme, CYP27B1, located in the kidney and other tissues. CYP24A1, located in all vitamin D-responsive tissues, catabolizes both calcifediol and calcitriol to inactive metabolites.

Excretion

Excretion of calcifediol occurs primarily through the biliary fecal route.

Specific Populations

Age, Gender and Race

Based on a population pharmacokinetic analysis, age, gender and race had no meaningful impact on steady-state concentrations of calcifediol following RAYALDEE administration.

Hepatic Impairment

The pharmacokinetics of RAYALDEE have not been investigated in patients with hepatic impairment.

Renal Impairment

Based on the population pharmacokinetics analysis, there was no meaningful difference in calcifediol steady-state concentrations following repeated RAYALDEE administration in patients with stage 3 or stage 4 chronic kidney disease.

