6.10 Efficacy Analyses

6.10.1 Primary Efficacy Endpoints

The two primary efficacy endpoints will be tested hierarchically to maintain an overall one-sided alpha level of 0.025. Therefore, the test of resolution of symptoms based on the aggregate FLU-PRO Plus[©] symptom score will be performed only if the attainment of serum 25D levels \geq 50 ng/mL at Day 14 is significant at <0.025.

The first primary efficacy endpoint, attainment of serum 25D levels at ≥50 ng/mL, will be assessed with a Chi-square statistic at Day 14. The serum 25D levels will also be compared between treatment groups at Days 7, 21 and 28 with a Chi-square statistic.

The second primary efficacy endpoint is the number of days to resolution of symptoms, defined as a reduction in the aggregate FLU-PRO Plus[©] score for the selected five COVID-19 symptoms recorded on Day 0 (prior to study drug initiation) to or below 5 for a minimum of three consecutive days. The time to resolution is defined as the number of days from Day 1 (study drug initiation) to the first day of achieving the aggregate ≤5 score for a minimum of three consecutive days, provided that no score greater than 5 is recorded between the two qualifying scores. Resolution will be determined by the first two successive qualifying scores which span a minimum of three consecutive days. For clarity, resolution will be considered as having been achieved if two successive aggregate scores of ≤5 are recorded on the first day of this occurrence and on a subsequent day that is at least two days (but not more than 5 days) later even if no score has been recorded between the two days. Missing symptom score values will be handled as described in Section 6.2. The number of days to resolution will be analyzed with a Cox proportional hazards model with covariates (baseline aggregate FLU-PRO Plus[©] score for the selected five COVID-19 symptoms, baseline serum 25D, and body weight).

As a sensitivity analysis of the resolution of symptoms, a tipping point approach will be used starting with the analysis in which scores are available for three consecutive days, with no missing interval, followed by increasing numbers of missing days in the up to five-day interval, that is, 1, 2 and 3 missing days between the two consecutive qualifying scores.

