Subgroup analyses for the primary efficacy endpoints will be based on age (\leq 40 or >40 years), severity of the selected five COVID-19 symptoms at baseline (aggregate FLU-PRO Plus[©] score of \leq or > the median score), attained serum 25D at Day 14 (below, within or above the targeted range of 50 to 100 ng/mL), body weight (\leq 100 or >100 kg), BMI (\leq 30 or >30), dosing compliance (<80% or \geq 80%), gender, race, ethnicity, number of comorbidities (<1 or \geq 1), duration of treatment (\leq 10 or >10 days) and prior or intercurrent COVID-19 vaccination and/or monoclonal antibody therapy for COVID-19.

In addition, the number of days to resolution of the five aggregated symptoms will be compared based on the serum 25D level at Day 14 (<50 ng/mL vs 50 to 100 ng/mL and 50 to 100 ng/mL vs >100 ng/mL), regardless of the assigned treatment group. The comparisons will be done using a Chi-square test. Frequency of relapses will be calculated, if possible, to account for potential worsening of symptoms after resolution (defined above), with relapse being defined as achieving an aggregate FLU-PRO Plus[©] score >5 for a minimum of three consecutive days.

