The severity, duration and clinical course of COVID-19 illness will be compared between treatment groups by analyzing changes in quality-of-life assessments recorded on the FLU-PRO Plus[©] questionnaire. Five of the six items from the questionnaire to be analyzed are: "Overall, how severe were your infection symptoms today?", "Overall, how were your infection symptoms today compared to yesterday?", "How much did your infection symptoms interfere with your usual activities today?", "Have you returned to your usual activities today?", "In general, how would you rate your physical health today?", and "Have you returned to your usual health today?" The scores for: symptom severity range from 0 (no infection symptoms today) to 4 (very severe); symptoms today range from 1 (much better) to 7 (much worse); symptom interference range from 1 (not at all) to 5 (very much). The first of two consecutive scores of ≤ 1 spanning at least three days and no more than five days will be considered the day of resolution, provided that no intervening scores of >1 are recorded. The scores for return to usual activities or health are either "yes" or "no", and the first occurrence of "yes" will be deemed to be day of resolution provided that a second "yes" is recorded no more than 5 days later without an intervening "no". The remaining sixth item to be analyzed is: "physical health range from 1 (poor) to 5 (excellent). The first of two consecutive scores of >4 spanning at least three days and no more than five days will be considered the day of resolution, provided that no intervening scores of <4 are recorded. Each item will be compared between treatment groups using a Cox proportional hazards model with covariates (aggregate FLU-PRO Plus[©] score for the selected five COVID-19 symptoms at baseline, serum total 25D at baseline, and body weight).

The clinical course of COVID-19 will be examined by subgroups defined by serum total 25D levels <50 ng/mL, 50 to 100 ng/mL and >100 ng/mL at Days 7, 14, 21 and 28.

 	

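### The only visible 25D subgroup for the primary endpoints is attained Day 14 25D, a post-randomisation measure; baseline 25D is collected but not pre-specified as an effect modifier

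*SAP*

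**What the plan says.** SAP 6.10.1 lists twelve subgroup factors for the two primary endpoints, and the Protocol repeats the list in the Synopsis and in 9.10.1. The 25D factor is "attained serum 25D at Day 14 (below, within or above the targeted range of 50 to 100 ng/mL". Neither baseline 25D nor kidney function is on the list. The nearest item is a count, less than one or at least one, in "gender, race, ethnicity, number of comorbidities".

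The other planned 25D analyses also use on-treatment levels. SAP 6.10.1 compares time to resolution across Day 14 25D bands "regardless of the assigned treatment group". In SAP 6.10.2 the clinical course is "examined by subgroups defined by serum total 25D levels" at Days 7, 14, 21 and 28.

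Baseline 25D is drawn at screening (Protocol 7.1.1). It enters the Cox model as a main effect, with covariates ending in "baseline serum 25D, and body weight". No product term with treatment is stated.

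Two background statements explain the interest. The Protocol Synopsis cites meta-analyses of supplementation against acute respiratory infection, "with those that were severely vitD deficient receiving the most benefit". Protocol 3.2 says: "Many subjects in each arm of this study may, therefore, have stage 3 or 4 CKD".

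**The concern.** A subgroup analysis of a randomised trial is interpretable because the factor is fixed before treatment, so the arms stay comparable within each level. Attained Day 14 25D does not meet that condition. Active subjects who remain below 50 ng/mL are a selected group, mainly those who started low or rose little, and they would be compared with nearly all of the placebo arm. Any difference mixes drug effect with selection. For symptom resolution there is a timing problem too: some subjects will have resolved before the sample that classifies them is taken.

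The natural randomised question is whether the effect varies with the 25D level a subject brings into the trial. The data for it are collected on every subject. If the analysis is not written down before unblinding, it will be post hoc, and the only pre-specified 25D subgroup will be one that cannot carry the interpretation readers will give it.

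**Working it through.** **Circularity for endpoint 1.** The endpoint is 25D of at least 50 ng/mL at Day 14, and the subgroup is cut at 50 ng/mL on the same sample. The response rate is 0% below the cut and 100% at or above it in both arms, by definition.

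**Imbalance for endpoint 2.** SAP 3.3 assumes at most 25% of control and more than 75% of active subjects reach 50 ng/mL, with 80 per arm. Its 19 per group for outcome 1 reproduces (power 90.2%). The rates are stated for Day 28; I apply them at Day 14.
- Below 50 ng/mL: placebo at least 0.75 × 80 = 60; active no more than 0.25 × 80 = 20.
- At or above 50 ng/mL: placebo no more than 20; active at least 60.

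**Who the active subjects below 50 are.** Protocol 3.2 gives a rise of 20 to 35 ng/mL from loading and 0.6 per maintenance dose. Ten maintenance doses (Days 4 to 13) add 6.
- Baseline 25: 25 + 20 + 6 = 51 to 25 + 35 + 6 = 66.
- Baseline 15: 15 + 20 + 6 = 41 to 15 + 35 + 6 = 56.

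Low starters therefore straddle the cut.

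**Size of the distortion (illustration).** A simulation used no drug effect on symptoms and baseline 25D with mean 22.5 (the middle of the Protocol's expected 20 to 25). The other inputs are assumptions: baseline SD 9, a uniform rise of 20 to 35 plus 6 on active drug only, and measurement noise SD 4. Below 50 ng/mL, mean baseline was 14.0 in active and 22.5 in placebo subjects. If baseline 25D is itself prognostic, spurious hazard ratios (HRs) follow:

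| Assumed HR for resolution per 10 ng/mL baseline | Active v placebo, below 50 | 50 to 100 v below 50, within active |
|---|---|---|
| 1.11 | 0.91 | 1.15 |
| 1.22 | 0.85 | 1.28 |
| 1.35 | 0.78 | 1.43 |

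An inert drug would appear harmful in those who miss the target and helpful in those who reach it.

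**What a baseline interaction could deliver.** Planned HR: ln(0.30)/ln(0.50) = 1.737, matching the stated 1.74. Events by Day 28: 80 × 0.50 + 80 × 0.70 = 96. (Schoenfeld power for the main comparison with 96 events is 77.4%, against the stated figure above 80%. That is a separate matter; only the event count is used here.)

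The detectable ratio of HRs at one-sided 0.025 and 80% power is exp[(1.960 + 0.842) × SE].
- Even two-way split, 48 events per stratum: SE = √(4/48 + 4/48) = 0.408; ratio = exp(2.802 × 0.408) = 3.1.
- 30% in the low stratum: 28.8 and 67.2 events; ratio 3.5. At 20%: 4.2. The documents give no split, so these shares are assumptions.
- Continuous, per SD: SE = √(4/96) = 0.204; ratio = exp(2.802 × 0.204) = 1.77. The 95% interval is the estimate divided and multiplied by exp(1.96 × 0.204) = 1.49.

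The figures 3.1 and 1.77 are on different scales. If baseline 25D were normal, the two halves of a median split would differ in mean by 2 × 0.798 = 1.6 SD, and 1.77 to the power 1.6 is about 2.5. The continuous term is thus more efficient (2.5 against 3.1), but still far from powered for modest effect modification.

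If constant hazards run to Day 42, events are 80 × (1 − 0.5^1.5) + 80 × (1 − 0.3^1.5) = 118.6, and the detectable ratios become 2.8 and exp(2.802 × √(4/118.6)) = 1.67.

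**The case against.** A reader might infer that the trial cannot validly test its own rationale that the most deficient benefit most. The documents do not support that.
- The greater benefit in deficient people is cited background from other trials. The stated hypothesis (Synopsis; Protocol 3.2) is that raising 25D to 50 ng/mL or more attenuates disease. No visible objective or endpoint concerns greater benefit in deficient subjects, and entry is not restricted by baseline 25D.
- The data are collected, so a valid interaction needs only one added term. What is missing is pre-specification.
- One cannot say that effect modification by baseline 25D is never estimated. The exploratory endpoints (Protocol 3.4.3) and the end of SAP 6.10.2 are redacted or blank, the Protocol contents list a section 9.10.4 that is not visible, and the SAP table list is described as not exhaustive.

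A reader might also infer a threefold kinetic difference in kidney disease from Protocol Appendix 2, section 12.3: "The mean apparent volume of distribution is 8.8 L in healthy subjects following a single oral dose of RAYALDEE, and 30.1 L" in stage 3 or 4 disease. The ratio 30.1/8.8 = 3.4 sets single dosing in healthy subjects against repeated dosing in patients, so population and regimen are confounded. It does not predict 25D levels in this trial. Nor does pooling subjects with and without kidney disease bias a 1:1 randomised comparison.

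Three further objections stand in part. Twelve factors in 160 subjects is already a long list, and more cuts add low-powered estimates. An interaction with baseline 25D would not isolate mechanism, because baseline 25D varies with adiposity, skin pigmentation and kidney function (Protocol 1.1 and 3.2). Some of these correlates, such as weight, BMI and race, are already subgroups. These points argue for one continuous term labelled exploratory. They do not rescue the attained-level subgroup.

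**Conclusion.** The concern holds in a limited form. The one visible 25D subgroup for the primary endpoints is post-randomisation, driven by treatment, and circular for endpoint 1; it cannot show whether the randomised effect differs by 25D status. Baseline 25D could show this, and it appears in the visible text only as a main effect.

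The stratum imbalance, at least 60 against no more than 20, rests on applying the Day 28 attainment bounds at Day 14. The simulated bias rests on assumed spread and prognostic strength and shows direction and plausible size only. The gain from the change is a valid, pre-specified estimate with an honest interval. Neither primary test nor the hierarchy is affected, so this is a worthwhile correction and not a threat to the trial's main conclusion.

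**What to change.** Amend SAP 6.10.1 before unblinding:
1. Add, as exploratory, one product of treatment with continuous baseline 25D in the Cox model for endpoint 2. Report the ratio of HRs with its 95% confidence interval and no claim of significance.
2. Add baseline 25D rows to the subgroup tables for both primary endpoints, for example below 20, 20 to below 30, and 30 ng/mL or above, which are the Protocol's own cuts in section 1.1. Show counts and events per cell, since some cells may be small.
3. State that analyses by attained 25D, including the comparison that ignores assigned arm and the clinical-course tables, are non-randomised and descriptive. Remove the attained-level subgroup for endpoint 1, where it is uninformative by construction.
4. Optionally, show 25D attainment and hypercalcaemia descriptively by screening eGFR below 60 against 60 or above, since the Protocol says many subjects may have stage 3 or 4 kidney disease.

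The cost is a paragraph of SAP text and a few table rows, with no new data. The downside is a few more imprecise exploratory estimates.

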3.5 Study Duration

The study is expected to be completed within approximately 8-12 weeks from the time of initial subject enrollment (first subject consented) to study completion for the last subject (last subject out/last visit complete). Each enrolled subject will participate in the study after randomization for up to 42 days (Day 1 through Day 42).

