5.3.2 Dose Reduction and Stopping Rules

Although hypercalcemia is unlikely given the extensive prior experience with Rayaldee (CTAP101 Capsules), any subject who exhibits a confirmed serum total calcium >10.5 and \leq 11.0 mg/dL (corrected for serum albumin) based on blood samples obtained on Days 7 and 14 will reduce the daily maintenance dose by one capsule (from 60 mcg to 30 mcg) starting at Day 21. The dose will similarly be reduced based on blood samples obtained on Days 7 and 14 if serum total 25D is confirmed to exceed 100 ng/mL, the maximum targeted level in the FDA-approved Package Insert for Rayaldee (see APPENDIX 2.), starting at Day 21.

Subjects who exhibit confirmed serum total calcium >11.0 mg/dL (corrected for serum albumin) based on blood samples obtained on Days 7, 14 and 21 will suspend dosing until normalization of serum calcium at which time (if applicable) dosing will be resumed at one capsule per day (30 mcg per day). Subjects will be requested to return to the clinic on the earliest possible day of their next scheduled visit (eg, Day 12 for the Day 14 visit) for the confirmatory blood draw.

Subjects who develop severe (CTCAE \geq 3) abnormalities (low or high) of serum phosphorus, uric acid or plasma iPTH will be withdrawn from study drug treatment but will continue in the study.

Enrollment of subjects into the study will be paused if mortality in the treatment arm is $\geq 7\%$ higher compared to the placebo arm until the Data Safety Monitoring Board (DSMB) makes an assessment about causality, and may resume once the DSMB deems it acceptable to continue (if applicable).

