6.9 Removal of Subjects from the Study or Study Drug / Stopping Criteria

The investigator may discontinue a subject from study drug treatment for any of the following reasons:

- A major protocol deviation occurs;
- A serious or intolerable AE occurs;
- The subject has a confirmed pregnancy;
- A clinically significant change in a laboratory parameter occurs (eg, increase in serum calcium above upper limit allowed); and,
- A clinically significant change in ECG at Visit 3 occurs as compared to baseline (eg, prolongation of QT interval).

The investigator may withdraw a subject from the study for any of the following reasons:

- The subject requests to be discontinued from the study (withdraws consent); or,
- The subject is lost to follow-up.

Subjects who develop severe (CTCAE \geq 3) abnormalities (low or high) of serum phosphorus, uric acid or plasma iPTH will be withdrawn from study drug treatment.

Enrollment of subjects into the study will be paused if mortality in the treatment arm is $\geq 7\%$ higher compared to the placebo arm until the DSMB makes an assessment about causality, and may resume once the DSMB deems it acceptable to continue (if applicable).

No subject replacement is planned. All subjects withdrawn from treatment will continue in the study until study completion and perform all assessments unless consent is withdrawn. The investigator will be requested to make all reasonable efforts to obtain clinical status at FU.

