Subgroup analyses for the primary efficacy endpoints will be based on age (≤ 40 or >40 years), severity of the selected five COVID-19 symptoms at baseline (aggregate FLU-PRO Plus[©] score of \leq or > the median score), attained serum 25D at Day 14 (below, within or above the targeted range of 50 to 100 ng/mL), body weight (≤ 100 or >100 kg), BMI (≤ 30 or >30), dosing compliance (< 80% or $\geq 80\%$), gender, race, ethnicity, number of comorbidities (< 1 or ≥ 1), duration of treatment (≤ 10 or >10 days) and prior or intercurrent COVID-19 vaccination and/or monoclonal antibody therapy for COVID-19.

In addition, the number of days to resolution of the five aggregated symptoms will be compared based on the serum 25D level at Day 14 (<50 ng/mL vs 50 to 100 ng/mL and 50 to 100 ng/mL vs >100 ng/mL), regardless of the assigned treatment group. The comparisons will be done using a Chi-square test. Frequency of relapses will be calculated, if possible, to account for potential worsening of symptoms after resolution (defined above), with relapse being defined as achieving an aggregate score >5 for a minimum of three consecutive days.

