3.2 Treatment Administration

Subjects will receive a loading dose (900 mcg Rayaldee or matching placebo) split into three equal doses of 300 mcg each administered on Days 1, 2 and 3, followed by 24 daily maintenance doses (60 mcg on Days 4 to 27) administered at bedtime after fasting for at least 3 hours following dinner.

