4.4 Per-Protocol Population

The per-protocol (PP) set, defined as subjects who do not have a major protocol deviation prior to resolution of the aggregated five symptoms, will also be used as supportive evidence of efficacy. Subjects who are non-compliant with the requirements of the protocol after achieving resolution of the five COVID-19 symptoms will be included in the PP set due to the expectation that such subjects will likely discontinue prematurely from the study.

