6.8 Prior and Concomitant Medications

Prior medications are defined as any continuing or new medication used within 12 weeks and discontinued before initiation of treatment on Day 1. Concomitant medications are defined as any continuing or new medication taken after treatment initiation on Day 1 or anytime thereafter until the end of the study. World Health Organization Drug Dictionary (WHODrug) Enhanced version September 2017, Format C, or later will be used to code concomitant and prior medications. Prior and concomitant medications will be tabulated by treatment group. All medications recorded on the eCRF, including start and stop (or ongoing as of) dates, AE number (if applicable), indication, dose, unit, route, and frequency will be listed.

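### The treatment-duration subgroup (≤10 or >10 days) is fixed after randomisation and depends partly on time to resolution, so it can distort that subgroup result; the vaccination/antibody factor merges baseline with on-study exposure

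*SAP*

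**What the plan says.** The final items of the subgroup list in SAP 6.10.1 are duration of treatment, cut at ≤ "10 or >10 days) and prior or intercurrent COVID-19 vaccination and/or monoclonal antibody therapy for COVID-19". Protocol 9.10.1 and the Protocol synopsis carry the same list; its last factor there reads "and prior or intercurrent COVID-19 vaccination and/or monoclonal antibody therapy for COVID-19". SAP Tables 14.2.1.11 and 14.2.1.12 present time to resolution by these subgroups. No interaction test, landmark rule or time-dependent handling is specified.

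Four other places bear on the point:

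- **Scheduled dosing** (SAP 3.2): the three-day loading dose is "followed by 24 daily maintenance doses (60 mcg on Days 4 to 27" in both arms. A duration of ≤10 days therefore arises only when dosing ends or is interrupted early.
- **Expected early exit** (SAP 4.4): non-compliance after resolution does not remove a subject from the per-protocol set, "due to the expectation that such subjects will likely discontinue prematurely from the study".
- **Other reasons to stop** (Protocol 5.3.2 and 6.9): confirmed high calcium "based on blood samples obtained on Days 7, 14 and 21 will suspend dosing until normalization of serum calcium". Severe phosphorus, uric acid or iPTH abnormalities, adverse events, ECG change, pregnancy and major deviations can also end dosing.
- **Follow-up after stopping drug** (Protocol 6.9): "All subjects withdrawn from treatment will continue in the study until study completion and perform all assessments unless consent is withdrawn".

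**The concern.** A subgroup can show whether a treatment effect differs between kinds of patient only if membership is settled before treatment can influence it. Duration of treatment is not. The SAP's own expectation links a short duration to having already resolved, and resolution is the event being analysed. Selecting the ≤10-day group therefore selects early resolvers in both arms, and within such a group there is little room left for the arms to differ.

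The table invites a question about how long treatment must last. If the drug works, the answer it gives could be largely an artefact of the split.

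The last factor has a related but milder fault. Prior vaccination or antibody is a baseline characteristic; intercurrent use happens on study. The list puts both under one item and, unlike the numerical factors beside it, states no levels. A result for that item would have no clear meaning.

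**Working it through.** **Inputs from the documents.** Resolution by Day 28 of 50% (control) and 70% (active), HR 1.74, 80 per group (SAP 3.3). Dosing Days 1-27 (SAP 3.2). Follow-up to Day 42 (Protocol 3.5: "Each enrolled subject will participate in the study after randomization for up to 42 days (Day 1 through Day 42").

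**Inputs assumed.** Exponential resolution times; the same HR for every subject; a share of resolvers who stop drug because they have resolved. The documents give no such share, so it is varied.

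**1. The plan's own figure.** ln(0.30)/ln(0.50) = 1.737, which reproduces the stated HR of 1.74.

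**2. Why the short-duration stratum hides an effect.**
- Control hazard = −ln(0.50)/28 = 0.0248 per day. Active hazard = 1.74 × 0.0248 = 0.0431 per day.
- Overall medians: 28 days for control and 28/1.74 = 16.1 days for active.
- A subject who stops 2 days after resolving falls in the ≤10-day stratum if resolved by Day 8. Probability F = 1 − exp(−8 × hazard): 18.0% control, 29.1% active.
- Median time among those early resolvers = −ln(1 − F/2)/hazard: 3.8 days control, 3.7 days active.

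A gap of about 12 days between medians shrinks to about 0.1 day because of the selection alone.

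**3. Simulated Cox hazard ratios within strata, true HR 1.74 for everyone.**

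| Stopping assumption | HR, ≤10 days | HR, >10 days |
|---|---|---|
| 25%, 50% or 100% of those resolved by Day 10 stop, equal in both arms | 1.04-1.07 | 1.72-1.74 |
| 25-75% of resolvers stop 2 days after resolution, plus 5% stopping at random; control resolution by Day 28 of 50% or 80% | 1.12-1.33 | 1.71-1.80 |
| As above, no random stopping | 0.93-1.13 | not listed separately |
| Stopping differs by arm, 30% control and 60% active | 1.03 | 1.54 |
| Stopping differs by arm, 60% control and 30% active | 1.03 | 1.93 |
| Comparison: a 15% split unrelated to outcome | 1.73 | 1.72 |

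Across the runs with stopping 2 days after resolution, the range is about 0.9-1.3 against 1.7-1.9. The last row shows that the gap comes from the way the strata are formed.

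The share resolved is also set by construction. With no unrelated stopping, the ≤10-day stratum is 100% resolved by Day 28; with 5% random stopping, 91-100% are resolved. In the first row's scenarios, 44-57% of the >10-day stratum are resolved by Day 28.

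**4. No drug effect (true HR 1.0).** With equal stopping, both strata show an HR of about 1.0. With unequal stopping (30% and 60%, either way round), the >10-day stratum shows 0.89 or 1.12 and the ≤10-day stratum about 1.0.

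**5. What would be seen in a trial of 160.**
- With half of resolvers stopping 2 days after resolution, the ≤10-day stratum holds about 80 × 0.180 × 0.5 = 7 control and 80 × 0.291 × 0.5 = 12 active subjects, before any other stoppers.
- A two-sided 5% test comparing the two stratum hazard ratios would reject in about 15% of trials (half of those resolved by Day 10 stop) to 22% (all stop) under HR 1.74, and in about 3% under no effect with equal stopping.

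**6. The vaccination/antibody factor.** No arithmetic applies. SAP 6.8 already separates exposure at first dose: "Prior medications are defined as any continuing or new medication used within 12 weeks and discontinued before initiation of treatment on Day 1". Medication taken after that point is concomitant. The subgroup list does not use this division.

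**The case against.** The strongest reply has four parts.

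- **Illness course is not the only driver of duration.** The protocol lists several safety and conduct reasons to stop drug, and resolution is not among them. This stands, and it weakens the link. It does not repair the split, because those reasons also arise after randomisation.
- **SAP 4.4 speaks of leaving the study, not of stopping drug.** Protocol 6.9 keeps the two apart. Leaving the study ends dosing, so the link is reasonable. But no passage says how many resolvers would leave, or that they would do so by Day 10. The size is therefore conditional on an assumption.
- **The consequences are limited.** Subgroups lie outside the hierarchical test, no claim is tied to them, and a stratum of about 19 subjects would look uninformative to a careful reader. This stands. The residual risk is that, with no interaction test planned, the two estimates are compared by eye.
- **The vaccination/antibody item may be meant as separate categories.** The text does not say that it is a single yes/no split. The supportable criticism is that the item names both exposures and gives no levels to separate them.

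A reader might go further and infer that the plan will produce a false interaction. The calculations do not support this: nothing appears without a drug effect when stopping is equal, and even under HR 1.74 a formal test would usually miss it. A reader might also infer that both factors are set by the course of the illness, or that intercurrent vaccination or antibody is rescue treatment. Prior exposure is a baseline factor, and the documents never describe intercurrent use as rescue.

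**Conclusion.** The point holds in limited form. Duration of treatment is a post-randomisation factor that the SAP itself connects with resolution, so it cannot show whether the effect on time to resolution depends on length of treatment. Under a uniform HR of 1.74, with 25-75% of resolvers stopping about 2 days after resolution, the split would show about 0.9-1.3 for ≤10 days and 1.7-1.9 for >10 days. If stopping differs between arms, the longer stratum can be biased in either direction.

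These figures rest on exponential times and on a stopping share that the documents do not give. What can be said is that the subgroup can distort, not that it will. The confirmatory alpha and the primary analyses are unaffected.

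The vaccination/antibody factor needs its levels defined. Attained 25D at Day 14 and dosing compliance, in the same list, are also post-randomisation and need the same caution.

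**What to change.** Amend SAP 6.10.1 and Protocol 9.10.1 (with the synopsis) before unblinding:

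- Remove duration of treatment as a subgroup for time to resolution. Report it descriptively by arm, with reasons for stopping, and state how suspended and resumed dosing is counted.
- Define the vaccination/antibody subgroup by status before the first dose, with stated levels, and list intercurrent use by arm as an on-study event. Do not rely on the 12-week window in SAP 6.8 for this, since an earlier vaccination would fall outside it.
- Label attained Day-14 25D and dosing compliance as post-randomisation, descriptive analyses that do not support causal treatment comparisons.

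The cost is SAP and protocol wording and changes to the shells of Tables 14.2.1.11 and 14.2.1.12. No new data should be needed if dates of vaccination and antibody treatment are recorded, as the existing subgroup already requires. The downside is the loss of one exploratory subgroup comparison. A baseline-25D subgroup could be added, but that is optional and not part of this correction.
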